5.2. Participant Dispositions

5.2.1. Definitions

5.2.1.2. Screened subjects / screening failures

Subjects are not screened for entry into the extension study. Screening information for the core study is reported in the core study CSR.

5.2.1.3. Subjects randomized/entered

The following variables are defined:

- **Randomized in the core study**: a subject is considered as randomized in the core study if randomization date and number are recorded in the core study. Randomization date is stored in SDTM201.DS.DSSTDTC where DS.DSDECOD='RANDOMIZED', randomization number is stored in SDTM201.DS.DSREFID When DS.DSTERM = RANDOMIZED. Treatment assignment is stored in SDTM.DM.ARM. Note: 2 subjects in the core study were randomized and not treated. These subjects will not be included in any analyses described in this SAP.
- **Randomized/entered TP1**: a subject is considered as randomized/entered in TP1 if they have a randomization/enrollment date entered for TP1. Randomization date is stored in SDTM202.DS.DSSTDTC where DS.DSSCAT='ENROLLMENT IN TP1'.
- **Randomized/entered TP2**: a subject is considered as randomized/entered in TP2 if they have a randomization/enrollment date entered for TP2. Randomization date is stored in SDTM202.DS.DSSTDTC where DS.DSSCAT='ENROLLMENT IN TP2'.
- Entered TP3: a subject is considered to have entered TP3 if they have a record in the study drug log (SDTM202.EC and SDTM202.SUPPEC) indicating transition to TP3.
- **Entered Follow-up Phase:** a subject is considered to have entered the Follow-up Phase if they have at least one Follow-up visit after EOT.

5.2.1.4. Subjects treated

The following variables are defined:

- Treated in the core study: a subject is considered to have been treated with ponesimod in the core study if they have at least one record in SDTM201.EC with a valid date/time (ECSTDTC) where EC.ECCAT = 'STUDY DRUG INTAKE', and with SDTM201.DM.ACTARM is 'Ponesimod 10 mg', 'Ponesimod 20 mg' or 'Ponesimod 40 mg'.
- **Treated in TP1**: a subject is considered to have been treated in TP1 if they have at least one record in SDTM202.EC with a valid date/time (ECSTDTC) where EC.ECCAT = 'STUDY DRUG INTAKE, which is on or after date randomized/entered into TP1 (SDTM202.DS.DSSTDTC where DS.DSSCAT = 'ENROLLMENT IN TP1').
- **Treated in TP2**: a subject is considered to have been treated in TP2 if they have at least one record in SDTM202.EC with a valid date/time (ECSTDTC) where EC.ECCAT = 'STUDY DRUG INTAKE, which is on or after date randomized/entered into TP2 (SDTM202.DS.DSSTDTC where DS.DSSCAT = 'ENROLLMENT IN TP2').

• **Treated in TP3**: a subject is considered to have been treated in TP3 if they have at least one record in SDTM202.EC with a valid date/time (ECSTDTC) where EC.ECCAT = 'STUDY DRUG INTAKE, which is on or after date entered into TP3.

5.2.1.5. Subject treatment completion status

A subject is considered to have completed treatment as per protocol in the core study if a treatment completion record is documented in SDTM201.DS, i.e., where DSSCAT = 'TREATMENT TERMINATION' and DSDECOD is equal to 'COMPLETED'. Date of completion is the date in DSSTDTC for this record.

A subject is considered to have prematurely discontinued from study treatment in the core study if a reason for premature treatment discontinuation or date of treatment discontinuation is documented in SDTM201.DS, i.e., where DSSCAT = 'TREATMENT TERMINATION' and DSDECOD is not equal to 'COMPLETED'. Date of discontinuation is the date in DSSTDTC for this record and reason for discontinuation is stored in DSDECOD.

Possible primary reasons for premature discontinuation of study treatment in the core study are 'Death', 'Adverse Event' and 'Other'. If the primary reason is 'Other', the specific reason is captured in DSTERM as free text.

A subject is considered to have completed treatment as per protocol in the extension study if a study completion record is documented in SDTM202.DS, i.e., where DSSCAT = 'TREATMENT TERMINATION' and DSDECOD is equal to 'COMPLETED'. Date of completion is the date in DSSTDTC for this record.

A subject who transitions to commercial study drug is considered to have completed study treatment as per protocol if DSSCAT = 'TREATMENT TERMINATION' and DSDECOD is equal to 'APPROVED DRUG AVAILABLE FOR INDICATION' in SDTM202.DS. Date of completion is the date in DSSTDTC for this record.

A subject is considered to have prematurely discontinued from study treatment in the extension study if:

• A permanent reason for discontinuation or date of discontinuation is documented in SDTM202.DS, i.e., where DSSCAT = 'TREATMENT TERMINATION' and DSDECOD is not equal to 'COMPLETED' or 'APPROVED DRUG AVAILABLE FOR INDICATION'. Date of discontinuation is the date in DSSTDTC for this record and the reason for discontinuation is stored in DSDECOD.

Possible primary reasons for premature discontinuation of study treatment in the extension study are 'Death', 'Lost to follow-up', 'Protocol specified withdrawal criterion met', 'Withdrawal by Subject', 'Physician decision' and 'Sponsor decision'. 'Withdrawal by Subject' is further categorized into: 'Tolerability related', 'Efficacy related', 'Other', and 'Not known'. Physician decision is further categorized into: 'Adverse event', 'Lack of efficacy/Treatment failure', and 'Other'. Sponsor decision is further categorized into 'Study terminated', and 'Other'.

If the subject or investigator decision reason is 'Other', the specific reason is captured in DSTERM as free text.

• A reason for premature treatment discontinuation is documented in the extension study, where subjects are considered to have prematurely discontinued if the last chronological

Statistical Analysis Plan AC-058B202

interval has in SDTM202.SUPPEC.QLABEL = 'Reason for treatment end' and SUPPEC.QVAL is 'Death', 'Adverse Event' or 'Other'.

If a subject has discontinued treatment but reason is missing, then this is coded to 'Reason not provided'.

Subjects who enter TP2 are considered to have completed treatment in TP1, and subjects who enter TP3 are considered to have completed treatment in TP2. However, subjects may complete treatment as per protocol in a given treatment period and elect not to proceed to the following treatment period. Such subjects have a record in the study drug log (EX/SUPPEX) where QLABEL = "Reason for treatment end" and QVAL = "END OF TREATMENT", and do not have a corresponding premature treatment discontinuation record in DS as defined above.

A subject is considered to have interrupted treatment for planned pregnancy if they have a record in SDTM.SUPPEX where QNAM = "REASTEND" and QVAL = "PLANNED PREGNANCY PER PROTOCOL".

All subjects who interrupted treatment for a planned pregnancy and have not yet restarted study treatment will have treatment status "Interrupted treatment for planned pregnancy". However, if a subject has restarted the treatment after the planned pregnancy interruption, they will be counted under their current treatment status either under "Prematurely Discontinued" or "Completed/Approved drug available".

An additional parameter "Restarted treatment after planned pregnancy interruption" will be summarized and will present all subjects interrupting the treatment due to planned pregnancy and restarting the treatment before the EOS date.

Interruptions for planned pregnancy are identified in the database as follows: Drug administration end date recorded on study drug log with reason for treatment end "PLANNED PREGNANCY PER PROTOCOL".

Restart of treatment after pregnancy are identified as follows: in the SV data set, the day of reinitiation is SVSTDTC for the record with SVUPDES = "RE-INITIATION OF STUDY DRUG X". This record should follow records with SVUPDES = "POST-PLANNED PREGNANCY".

The following variables are derived for treatment completion/discontinuation:

- Treatment completed in the core study;
- Treatment prematurely discontinued in the core study;
- Reason for premature treatment discontinuation in the core study;
- Treatment completed in TP1;
- Treatment prematurely discontinued in TP1;
- Reason for premature treatment discontinuation in TP1;
- Treatment completed in TP2;
- Treatment prematurely discontinued in TP2;
- Reason for premature treatment discontinuation in TP2;
- Interrupted treatment for planned pregnancy in TP2;

CONFIDENTIAL – FOIA Exemptions Apply in U.S.

- Re-started treatment after planned pregnancy interruption in TP2;
- Treatment completed in TP3;
- Availability of commercial ponesimod in TP3 (as a subcategory of "Treatment completed in TP3")
- Treatment prematurely discontinued in TP3;
- Reason for premature treatment discontinuation in TP3;
- Interrupted treatment for planned pregnancy in TP3;
- Re-started treatment after planned pregnancy interruption in TP3;

For subjects who discontinued from study treatment, the time of treatment discontinuation (in days) is defined as:

- (Date of treatment discontinuation (in either the core or extension study) date of first ponesimod administration + 1 day) (End date of pregnancy interruption Start date of pregnancy interruption + 1 day), for subjects with planned pregnancy interruption and restart of the treatment,
- (Date of treatment discontinuation (in either the core or extension study) date of first ponesimod administration ponesimod start date + 1 day), for all other subjects.

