3.6.2 Study drug interruption

Study drug interruption should be avoided.

If study drug intake is interrupted by the patient for any reason, she/he must immediately inform the primary investigator / treating neurologist.

Study drug may be temporarily interrupted in response to an AE, a diagnostic or therapeutic procedure, a laboratory abnormality, a planned pregnancy, or for administrative reasons. The permitted maximum duration of the study drug interruption is 81 weeks for planned pregnancies and 12 weeks for other reasons (if exceeded, the patient will then be prematurely discontinued from the study).

In the event of a re-initiation of study drug, one tablet of ponesimod 2, 3, 4, 5, 6, 7, 8, 9, or 10 mg will be taken orally o.d. during the uptitration period (Day 1 to 14). During the maintenance period, patients will continue to take one tablet of ponesimod 20 mg orally o.d. [Table 6]. If a blister kit with the starting dose of 2 mg is not available at the site, re-initiation should be delayed until it becomes available (temporary treatment interruption).

Detailed guidance on how to re-initiate study drug in the event of drug interruption is provided in Appendix 5.

EudraCT 2009-011470-15 EDMS-ERI-206617631

Ponesimod / ACT-128800 / JNJ-67896153 Multiple Sclerosis Protocol AC-058B202 Version 12 15 March 2022, page 68/179

Confidential

Treatment period	Duration	Dose regimen
Titration	Day 1 and 2	2 mg
Titration	Day 3 and 4	3 mg
Titration	Day 5 and 6	4 mg
Titration	Day 7	5 mg
Titration	Day 8	6 mg
Titration	Day 9	7 mg
Titration	Day 10	8 mg
Titration	Day 11	9 mg
Titration	Day 12 to 14*	10 mg
Maintenance	Day 15 until EOT3	20 mg

Table 6:2-week gradual uptitration regimen

* An additional visit 14 days (± 1 day) after the day of re initiation (Re initiation Day 15) is mandated for patients with cardiovascular risk factors [see Appendix 5], but may be scheduled for any patient at the discretion of the investigator / treating neurologist. The titration kit will therefore include 3 additional tablets (to be used if applicable) for treatment on Day 15 17 (i.e., dose regimen 20 mg).

EOT3 End of Treatment

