If a patient becomes pregnant while on study drug, study drug must be immediately and permanently discontinued. The investigator must counsel the patient and discuss the risks of continuing with the pregnancy and the possible effects on the fetus.

Planned pregnancy:

Female patients participating in the study and wishing to become pregnant during the study may stay in the study and will have the study drug interrupted prior to pregnancy and reinitiated after delivery.

Before becoming pregnant, the following protocol requirements must be met:

- The wish to become pregnant and stay in the study has to be communicated by the female patient to the primary investigator / treating neurologist during a scheduled visit occurring no later than at Visit P28 (Week 324). If the wish to become pregnant is communicated after Visit P28 (Week 324), the study drug interruption for a planned pregnancy would not be allowed.
- Prior to interrupting contraception, the patient must have 2 negative urine pregnancy tests: one at the scheduled visit on the day of study drug interruption and one 30 days after study drug interruption.
- The total duration of the study drug interruption due to planned pregnancy must not exceed 81 weeks, otherwise the study drug will be discontinued.
- The patient must agree to be followed by an appropriate health care professional (e.g., gynecologist, obstetrician and/or midwife) during pregnancy according to local practice, to have the reports from pregnancy assessments communicated to the primary investigator / treating neurologist and to have the information on the patient's MS status communicated by the primary investigator / treating neurologist to that health care professional.

In addition to the protocol requirements above, the primary investigator / treating neurologist must explain the following to the patient:

- The potential impact of pregnancy and post-partum period on the patient's MS and potential medical treatments that would be available for the patient while the study drug is interrupted;
- Re-initiation of study drug can only take place after delivery and after breastfeeding has been stopped, if applicable, and will require a medical evaluation of patient's eligibility for study drug re-initiation;
- Timing of the interruption and possible re-initiation of study drug and of contraception, related pregnancy tests and unscheduled visits;
- The need for re-uptitration at the study drug re-initiation;

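### The final disposition rules keep an open 'interrupted for planned pregnancy' status that the protocol timeline has closed, and set no precedence over the rule that defines premature discontinuation

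*SAP*

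**What the plan says.** SAP 5.2.1.5 contains two rules that can apply to the same woman.

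- **Record-based rule.** A subject in the extension has prematurely discontinued treatment if the disposition dataset (DS) holds a termination record "where DSSCAT = 'TREATMENT TERMINATION' and DSDECOD is not equal to 'COMPLETED' or 'APPROVED DRUG AVAILABLE FOR INDICATION". The reason is read from that record. Pregnancy is not mentioned as an exception.
- **Pregnancy rule.** "All subjects who interrupted treatment for a planned pregnancy and have not yet restarted study treatment will have treatment status" *Interrupted treatment for planned pregnancy*. By contrast, "if a subject has restarted the treatment after the planned pregnancy interruption, they will be counted under their current treatment status", meaning either prematurely discontinued or completed (including approved drug available).

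SAP 5.2.2 tabulates interrupted, restarted, completed, prematurely discontinued and reason as separate entries. It does not say whether they are mutually exclusive.

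The protocol limits these interruptions. Section 3.6.2 sets the limit: "The permitted maximum duration of the study drug interruption is 81 weeks for planned pregnancies and 12 weeks for other reasons". It then gives the consequence of a longer interruption: "if exceeded, the patient will then be prematurely discontinued from the study". Appendix 1, section D: "The total duration of the study drug interruption due to planned pregnancy must not exceed 81 weeks, otherwise the study drug will be discontinued". The same appendix sets the last date for declaring the wish: "If the wish to become pregnant is communicated after Visit P28 (Week 324), the study drug interruption for a planned pregnancy would not be allowed".

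**The concern.** The pregnancy rule describes someone whose status is still undecided. At an interim data cut that is a real state. At final lock it should not be, because the protocol forces every such interruption to end in a restart, a discontinuation, or completion through commercial availability.

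The SAP has no step that moves a non-restarter out of the open status, and it does not say which of its two rules wins. Premature discontinuation and its reasons are basic retention outputs of a long uncontrolled extension. Two programmers following this section in good faith could report different percentages and different reason tables.

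**Working it through.** **1. Can a permitted interruption still be open at final lock?**

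Inputs: Visit P28 is Week 324 (Protocol 3.12.3.2; check: 27 intervals × 12 weeks = 324). The maximum interruption is 81 weeks (Protocol 3.6.2). TP2 and TP3 together last up to 540 weeks.

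- Latest limit: 324 + 81 = Week 405, which is 540 − 405 = 135 weeks before the end.
- If the drug is stopped one 12-week visit after the declaration: 324 + 12 + 81 = Week 417, still 123 weeks before the end.

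In calendar time, take slow assumptions: last patient first visit on 30 June 2011 (the synopsis gives Q2 2011), a full 96-week TP1, 14 days of visit window at the end of TP1 and again at P28, and a 3-month gap (92 days) before P1.

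- P1: 30 June 2011 + 96 weeks + 14 days + 92 days = 16 August 2013.
- P28: + 324 weeks + 14 days = 15 November 2019.
- 81-week limit: 4 June 2021, or 27 August 2021 with the extra visit.
- Gap to the SAP date of 20 September 2023: about 120 weeks, or about 108 weeks.

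No interruption within protocol limits can still be open.

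**2. What happens to a non-restarter under each rule?**

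| How the SAP is programmed | Interrupted row | Premature discontinuation and reason |
|---|---|---|
| Pregnancy rule overrides | counted | not counted |
| Record-based rule overrides (record neither completed nor approved drug) | not counted, or descriptive only | counted |
| Both applied | counted | counted |

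The study-drug-log route in SAP 5.2.1.5 does not settle the matter. It requires the last interval to end for death, adverse event or other. A non-restarter's last interval is coded as planned pregnancy.

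**3. Size.**

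The documents give no count of non-restarters, so only the weight of each woman can be shown. At most 464 − 2 = 462 subjects received ponesimod (464 randomized in the core study, Protocol 1.3.2.3; 2 not treated, SAP 5.2.1.3). For *k* women the shift is 100 × *k* / 462 percentage points:

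- *k* = 0: 0
- *k* = 1: 0.22
- *k* = 5: 1.08
- *k* = 10: 2.16

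These values of *k* are illustrations. The by-period tables in SAP 5.2.2 divide by subjects treated in that period, a smaller number, so each woman weighs more there.

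**4. Time to discontinuation.**

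SAP 5.2.1.5 subtracts the interruption only "for subjects with planned pregnancy interruption and restart of the treatment". For a non-restarter, any off-drug time between last dose and the recorded discontinuation date stays in the variable. The documents do not show how those dates are recorded.

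**The case against.** A reader might infer that discontinuations are in fact under-counted and the percentage is too favourable. The documents do not establish that. The record-based rule has no pregnancy exemption, and SAP 5.2.2 never says the rows exclude each other, so a non-restarter with a termination record may be counted correctly or in two places. The under-count follows only if the pregnancy rule overrides.

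A reader might also take every non-restarter to be a premature discontinuation by protocol. That is too broad. Sections 3.6.2 and Appendix 1 apply once 81 weeks are exceeded. Under Protocol 1.4.6, a patient whose country gains commercial ponesimod is treated as a completer, and SAP 5.2.1.5 follows this.

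Nor are these women hidden. The interrupted row is displayed, so even on the literal reading completed, discontinued and interrupted together account for them. Showing pregnancy apart from tolerability or efficacy withdrawals is a fair presentation choice.

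The time-to-discontinuation variable matters little here. SAP 5.2.2 still describes a Kaplan-Meier plot of it, but SAP 6.2.3 says the plot will not be presented in the Final CSR, and SAP 5.2.2 specifies no other summary of it. AP3 exposure ends at the last ponesimod dose (SAP Table 10), so trailing off-drug time does not enter there.

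Finally, the remark in SAP 6.2.3 about a rule kept from a 2022 snapshot concerns the exposure and safety exclusions of SAP 5.1.3. It does not show that the disposition status came from that snapshot.

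All of this limits the consequence. It does not supply the missing precedence or make the open status valid at final lock.

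**Conclusion.** The point stands as a conflict of rules. The final SAP assigns non-restarters to a status that matches no state the protocol allows at lock, and that assignment conflicts with the SAP's own record-based definition without a stated order. Depending on programming, a non-restarter whose record shows discontinuation is left out of the discontinuation count and reasons, or shown in two rows.

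The timing conclusion rests on the protocol's own limits and has more than two years to spare. The effect on results is unknown: it is nil if there are no such women, and at least about 0.22 percentage points for each affected woman if the pregnancy rule overrides. This is a minor point of definition and does not show that the reported retention is biased.

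**What to change.** Add to SAP 5.2.1.5 for the Final CSR:

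- Each non-restarter's final treatment status comes from the existing completion and discontinuation rules of that section, with the DS treatment-termination record taking precedence. She is prematurely discontinued with the recorded reason, or completed if the record says completed or approved drug available.
- 'Interrupted for planned pregnancy, not restarted' is kept as a descriptive, non-exclusive row under whichever category applies. SAP 5.2.2 should say that it is not a separate final status.
- If the time-to-discontinuation variable is still derived, it ends at the last ponesimod dose for non-restarters. SAP 5.2.2 should also be brought into line with SAP 6.2.3 on the dropped Kaplan-Meier plot.

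The cost is a few sentences of SAP text and a small change to disposition programming. No new data are needed. The discontinuation percentage may rise slightly or not at all.

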5.2.1.6. Subject study completion status

A subject is considered to have completed study in either the core or the extension if they completed the EOS Visit as per protocol. This definition is independent of treatment completion, i.e., a subject can prematurely discontinue from treatment but complete the study.

A subject is considered to have completed the core study as per protocol if a study completion record is documented in SDTM202.DS, i.e., where DSSCAT='STUDY TERMINATION' and DSDECOD is equal to 'COMPLETED'. Date of completion is the date in DSSTDTC for this record.

A subject is considered to have prematurely discontinued from the core study if a permanent reason for study discontinuation or date of study discontinuation is documented in SDTM201.DS, i.e., where DSSCAT = 'STUDY TERMINATION' and DSDECOD is not equal to 'COMPLETED'. Date of core study discontinuation is the date in DSSTDTC for this record and reason for discontinuation is stored in DSDECOD.

Possible main reasons for premature discontinuation in the core study are 'Death', 'Withdrawal of subject's consent', 'Lost to follow-up' and 'Administrative reason'.

A subject is considered to have completed the extension study as per protocol if a study completion record is documented in SDTM202.DS, i.e., where DSSCAT = 'STUDY TERMINATION' and DSDECOD is equal to 'COMPLETED'. Date of completion is the date in DSSTDTC for this record. A subject is considered to have completed study per protocol in a given period if they entered the period and completed the extension study whilst in that period.

A subject who transitions to commercial study drug is considered to have completed the extension study as per protocol and if DSSCAT = 'STUDY TERMINATION' and DSDECOD is equal to

Statistical Analysis Plan AC-058B202

'APPROVED DRUG AVAILABLE FOR INDICATION' in SDTM202.DS. Date of completion is the date in DSSTDTC for this record.

A subject is considered to have prematurely discontinued from the extension study if a reason for premature study discontinuation or date of study discontinuation is documented in SDTM202.DS, i.e., where DSSCAT = 'STUDY TERMINATION' and DSDECOD is not equal to 'COMPLETED' or 'APPROVED DRUG AVAILABLE FOR INDICATION'. Date of extension study discontinuation is the date in DSSTDTC for this record and reason for discontinuation is stored in DSDECOD.

Possible main reasons for premature discontinuation from the extension study are 'Death', 'Lost to follow-up', 'Withdrawal by Subject', 'Physician decision', 'Sponsor decision'. 'Withdrawal by Subject' is further categorized into: 'Tolerability related', 'Efficacy related', 'Other' and 'Not Known'. Physician decision is further categorized into: 'Adverse event', 'Lack of efficacy/Treatment failure', and 'Other'. Sponsor decision is further categorized into 'Study terminated', and 'Other'.

If the subject, investigator or sponsor decision reason is 'Other', the specific reason is captured in DS.DSTERM as free-text.

The following variables are defined for study completion/discontinuation:

- Completed the core study as per protocol;
- Prematurely discontinued study in the core;
- Reason for premature discontinuation in the core study;
- Completed the core study as per protocol and not entered in the extension;
- Completed TP1 as per protocol;
- Prematurely discontinued study in TP1;
- Reason for premature study discontinuation in TP1;
- Completed TP1 as per protocol and not entered in TP2;
- Completed TP2 as per protocol;
- Prematurely discontinued study in TP2;
- Reason for premature study discontinuation in TP2;
- Completed TP2 as per protocol and not entered in TP3;
- Completed TP3 as per protocol;
- Availability of commercial ponesimod in TP3*
- Prematurely discontinued study in TP3;
- Reason for premature study discontinuation in TP3;

*This will not be listed as a reason for premature study discontinuation as this is considered study completion as per protocol provided the subject had an EOS2 or EOS3 assessment.

